12.1.2. Deaths

All deaths, as well as deaths within 30 days after last dose of study treatment, will be tabulated.

12.1.3. Adverse Events of Special Interest

BMS provided EORTC with a list of adverse events of special interest (AESIs). The categories for AESIs are as followed which are defined by MedDRA SMQs, HLTs, and PTs

- 1) Ataxia including Fall, Gait Disturbances, and Balance Disorders/Dizziness
- 2) Dysarthria
- 3) Hallucination/Delirium

Unless otherwise specified, summaries of treatment-emergent AESIs will be provided for the whole study time and per period, overall and per treatment arm.

Overall summaries of AESIs will be provided for:

- subjects with at least one AESI;
- subjects with at least one AESI related to any study drug;
- subjects with at least one serious AESI (SAE);
- subjects with at least one serious AESI (SAE) related to any study drug;
- subjects with at least one CTCAE Grade 3 or 4 AESI;
- subjects with at least one CTCAE Grade 3 or 4 AESI related to any study drug;
- subjects with at least one AESI leading to death;
- subjects with at least one AESI related to any study drug leading to death;
- subjects with at least one AESI leading to dose reduction,
- subjects with at least one AESI leading to dose interruption
- subjects with at least one AESI leading to study drug withdrawal;

In addition, treatment-emergent AESIs will be summarized per AESI category and per PT for the followings:

- all AESIs;
- AESIs related to any study drug;
- CTCAE Grade 3 or 4 AESIs;

- CTCAE Grade 3 or 4 AESIs related to any study drug;
- AESIs by age group , for the whole study and overall;
- AESIs by sex, for the whole study and overall;
- AESIs by race, for the whole study and overall;
- Serious AESIs (SAEs);
- Serious AESIs (SAEs) related to any study drug;
- AESIs leading to death;
- AESIs leading to death related to any study drug;
- AESIs leading to dose reduction;
- AESIs leading to dose interruption;
- AESIs leading to study drug withdrawal.

12.2. Clinical Laboratory Evaluations

This study will use the International CTCAE, version 5.0 for grading of applicable laboratory tests. Normal ranges will be used to determine the categories of below and above normal ranges for lab tests that have no severity grade. Hematological and biochemistry adverse events will be assessed on the basis of at least monthly blood counts. The worst grades during the treatment period will be summarized by treatment arm. Listings of clinical laboratory data from central laboratory with abnormal flags will be provided by subjects and tests. Listings will also be provided for the local laboratory data. The nadir and overall nadir will be presented with median, range (minimum, maximum), IQR, mean and standard deviation.

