### 3.1 Inclusion Criteria

- Histologically confirmed newly diagnosed glioblastoma (WHO grade IV)
- Tumor resection (gross total or partial), or open biopsy only (stereotactic biopsy not allowed)
- Availability of FFPE tumor block or 24 unstained slides for MGMT analysis
- Patient must be eligible for standard TMZ/RT→TMZ
- Karnofsky performance score (KPS)  $\geq 70$  (Appendix E)
- Recovered from effects of surgery, postoperative infection and other complications of surgery (if any)
- The patient is at least 18 years of age on day of signing informed consent
- Stable or decreasing dose of steroids for at least 1 week prior to inclusion
- The patient has a life expectancy of at least 3 months
- Patient has undergone a brain MRI within 14 days of randomization but after intervention (resection or biopsy)
- The patient shows adequate organ functions as assessed by the specified laboratory values within 2 weeks prior to randomization defined as adequate bone marrow, renal and hepatic function within the following ranges:
  - WBC  $\geq 3 \times 10^9/L$
  - ANC  $\geq 1.5 \times 10^9/L$
  - Platelet count of  $\geq 100 \times 10^9/L$  independent of transfusion
  - Hemoglobin  $\geq 10$  g/dl
  - Total Bilirubin  $\leq 1.5$  ULN
  - ALT, AST, alkaline phosphatase (ALP)  $\leq 2.5 \times$  ULN

- Serum creatinine < 1.5 x ULN or creatinine clearance (CrCl) > 30 mL/min (using the Cockcroft-Gault formula)
- Women of child bearing potential (WOCBP - refer to Appendix H for definition) must have a negative urine or serum pregnancy test within 7 days prior to randomization
- Patients of childbearing / reproductive potential must agree to use adequate birth control measures, as defined by the investigator, during the study treatment period and for at least 6 months after the last study treatment. A highly effective method of birth control is defined as those which result in low failure rate (i.e. less than 1% per year) when used consistently and correctly (see Appendix H). Patients must also agree not to donate sperm during the study and for 6 months after receiving the last dose of study treatment.
- Women who are breast feeding must agree to discontinue nursing prior to the first dose of study treatment and until 6 months after the last study treatment.
- Ability to take oral medication

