#### Hematological and biochemistry parameters

All laboratory values will be graded. The worst grade of each hematological and biochemistry parameter will be calculated for each patient. Frequencies and percentages of grade 1, 2, 3, 4 in each category will be tabulated. A column with pooled grade 3/4 frequencies and percentages will also be displayed.

In a separate table, the frequencies and percentages of patients with at least one grade ( $\geq 1$ ) or one grade 3/4 hematological or biochemistry toxicity will be presented.

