12.1.1. Treatment-emergent adverse events (TEAEs)

Adverse events will be analyzed in terms of TEAEs which are defined as AEs occurring or worsening on or after the date of start of treatment and within 30 days after the last treatment administration. AEs present at baseline which resolve during treatment and occurred again (at any grade) are considered TEAEs. AEs present at baseline which did not resolve within 30 days of the last treatment or which resolved but did not occur again are excluded from TEAEs.

Unless otherwise specified, summary of TEAEs will be provided for the whole study time and per period, overall and per treatment arm.

An overall summary of TEAEs will be provided for:

- subjects with at least one TEAE;
- subjects with at least one TEAE related to any study drug;
- subjects with at least one treatment-emergent serious AE (SAE)
- subjects with at least one treatment-emergent serious AE (SAE) related to any study drug;
- subjects with at least one CTCAE Grade 3 or 4 TEAE;
- subjects with at least one CTCAE Grade 3 or 4 TEAE related to any study drug;
- subjects with at least one TEAE leading to death (Grade 5);
- subjects with at least one TEAE leading to death (Grade 5) related to any study drug;
- subjects with at least one TEAE leading to dose reduction;
- subjects with at least one TEAE leading to dose interruption;
- subjects with at least one TEAE leading to study drug withdrawal;

In addition, TEAEs will be summarized per SOC and per PT for the following:

- all TEAEs;
- TEAEs, occurring for more than 10% of subjects in any treatment group;
- TEAEs related to any study drug (TMZ, MRZ);
- CTCAE Grade 3 or 4 TEAE;
- CTCAE Grade 3 or 4 TEAE related to any study drug;
- TEAEs by age group, for the whole study time only;
- TEAEs by sex, for the whole study time only;
- TEAEs by race, for the whole study time only;
- Treatment-emergent serious AEs (SAEs);
- Treatment-emergent serious AEs (SAEs) related to any study drug;
- TEAEs leading to death;
- TEAEs related to any study drug leading to death;
- TEAEs leading to dose reduction;
- TEAEs leading to dose interruption;
- TEAEs leading to study drug withdrawal.

Subjects with multiple occurrences of the same event will be counted only once per subject for each summary. Results will be reported in descending order of overall subject frequency in the overall column (unless otherwise specified) by SOC and by PT within the SOC. For summaries

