12.2.1. Hematology

In order to investigate the maximal degree of myelosuppression, absolute neutrophil counts (ANC), white blood cell counts (WBC), platelet counts, and hemoglobin will be summarized by worst grade overall for each subject. Frequencies and percentages of Grade 1, 2, 3, 4 in each category will be tabulated. A column with pooled Grade 3/4 frequencies and percentages will also be displayed. In a separate table, the frequencies and percentages of subjects with at least one Grade ≥ 1 or one Grade 3 or 4 hematological toxicity will be presented.

For erythrocytes and hematocrit normal ranges will be used to determine the categories of below and above normal ranges.

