12.3. Vital Sign/Physical Examination Measurements

For vital signs, the shift from baseline to worst during the treatment in below, within, and above the normal ranges will be displayed in cross-tabulations for each treatment. Summary statistics (N, Mean, Standard Deviation, Median, Minimum, and Maximum) of observed values and change from baseline values will be presented.

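### Laboratory toxicity counts take the worst on-treatment grade without the baseline grade, so unchanged entry abnormalities can enter the any-grade tables and weaken the relative contrast between arms

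*SAP*

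**What the plan says.** SAP 12.2 grades laboratory tests by CTCAE v5.0 and states: "The worst grades during the treatment period will be summarized by treatment arm". For hematology, SAP 12.2.1 adds that "the frequencies and percentages of subjects with at least one Grade ≥ 1 or one Grade 3 or 4 hematological toxicity will be presented". SAP 12.2.2 does the same for hematology and biochemistry combined. Protocol 8.2.3.2 has the same rule: "The worst grade of each hematological and biochemistry parameter will be calculated for each patient". None of these sections refers to the grade at entry.

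Other safety data in the same SAP do refer to baseline. Treatment-emergent adverse events are those "which are defined as AEs occurring or worsening on or after the date of start of treatment" (SAP 12.1.1), and an event present at baseline that persists unchanged is left out. For vital signs, SAP 12.3 plans that "the shift from baseline to worst during the treatment in below, within, and above the normal ranges will be displayed", and SAP 12.4 plans the equivalent table for ECG interpretation.

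Baseline laboratory data are not ignored altogether. Protocol 8.2.3.2 presents baseline laboratory grades with the other baseline data in the ITT population, and SAP 9.1 lists hematology and biochemistry values among the baseline characteristics. SAP 6.1 mentions mean changes in laboratory parameters, but SAP 12.2 has no table for them.

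**The concern.** Protocol 3.1 lets patients enter with hemoglobin from 10 g/dl, platelets from 100 x 10^9/L, bilirubin up to 1.5 x ULN, and ALT, AST and ALP up to 2.5 x ULN. The renal criterion is an either/or: "Serum creatinine < 1.5 x ULN or creatinine clearance (CrCl) > 30 mL/min". A patient can therefore exceed the creatinine limit and qualify on clearance, or the reverse. No numeric entry limit is set for sodium, potassium, calcium, magnesium, albumin or glucose, all of which SAP 12.2.2 summarizes by worst grade.

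If such a value counts as Grade 1 or more at entry and stays there, the patient appears in the toxicity table although nothing happened on treatment. The same finding recorded as an adverse event would not be treatment-emergent. What is at stake is how the any-grade laboratory tables read in the primary and long-term reports: a background that has nothing to do with treatment is labelled toxicity in both arms, and a real relative increase on marizomib looks smaller.

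**Working it through.** The documents give no expected laboratory toxicity rate, so there is no planned figure to reproduce. The check is an illustration. Every rate in it is an assumption; only the counting rules come from the plan.

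**Inputs (assumed).**
- b: share of patients at Grade 1 or more at entry who stay there.
- p: rate of new abnormality among patients normal at entry, 10% in control and 20% on marizomib (true risk ratio 2.0).

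**Formulas, per arm.**
- Planned any-grade rate = b + (1 − b)p.
- Worsened-from-baseline rate, if patients abnormal at entry never change = (1 − b)p.
- Worsened-from-baseline rate, if they worsen as often as normal patients become abnormal = bp + (1 − b)p = p.

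Example at b = 20%: planned control 0.20 + 0.80 × 0.10 = 28%; planned marizomib 0.20 + 0.80 × 0.20 = 36%. Risk ratio 36/28 = 1.29; difference 8 points.

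| b | Planned table | Worsened, entry-abnormal never change | Worsened, entry-abnormal also worsen |
|---|---|---|---|
| 10% | 19 v 28%, RR 1.47, diff 9 | 9 v 18%, RR 2.0, diff 9 | 10 v 20%, RR 2.0, diff 10 |
| 20% | 28 v 36%, RR 1.29, diff 8 | 8 v 16%, RR 2.0, diff 8 | 10 v 20%, RR 2.0, diff 10 |
| 30% | 37 v 44%, RR 1.19, diff 7 | 7 v 14%, RR 2.0, diff 7 | 10 v 20%, RR 2.0, diff 10 |

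Unchanged patients add b to both arms. The ratio shrinks, while the difference is (1 − b) times the difference in p under either rule. The planned table understates the difference only in the last column, where patients abnormal at entry also worsen more on marizomib. A move from Grade 1 to Grade 2 leaves the any-grade line unchanged.

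Other assumed rates give the same pattern. With 20% v 30% (true ratio 1.50), the planned risk ratio is 1.32, 1.22 and 1.12 at b = 10, 20 and 40%. The planned differences are 9, 8 and 6 points, identical to the worsened count when patients abnormal at entry never change.

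**Chance imbalance at entry.** The share b can itself differ between arms, with a 95% range of ±1.96 × √(2b(1 − b)/n). At b = 20% this is ±5.7 points with 375 per arm (SAP 5.1 target) and ±6.3 points with 308 per arm (616 randomized at the primary cutoff, split evenly). A fraction 1 − p of any such imbalance passes into the planned any-grade difference.

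**Can the separate baseline table repair this?** No. It is a marginal table in the ITT population. The toxicity tables use the safety population by treatment received, and SAP 6.2.2 moves a marizomib-arm patient who took temozolomide but no marizomib to control. Within-patient worsening cannot be recovered from two marginal tables on different populations.

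**The case against.** The strongest reply is that worst grade is the right summary for its stated purpose, since SAP 12.2.1 wants the maximal degree of myelosuppression. Grades 1 to 4 are shown separately with a pooled Grade 3/4 column, and nadir summaries, listings and baseline data are also planned. All of that stands, and it is why the worst-grade tables should stay. It does not supply a view of change from entry.

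A second reply also stands in part. CTCAE v5.0 and the site normal ranges are not in the documents. The grade at each eligibility limit, and whether some grades already allow for an abnormal baseline, cannot be checked here. The point holds only for parameters whose grade is not baseline-relative.

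Four stronger readings are tempting but not supported:

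- That the planned tables shrink the absolute difference. Unchanged patients alone do not do this, as the working shows.
- That the Grade 3/4 counts are distorted. Some analytes have no entry limit, so entry at a high grade is not formally excluded, but nothing in the documents shows that it occurs.
- That the laboratory and adverse event tables contradict each other. One reports measured values and the other reported events, so different counts are not in themselves an inconsistency.
- That the safety conclusion is at risk. The adverse events of special interest are ataxia, dysarthria and hallucination/delirium (SAP 12.1.3), and the IDMC's stated concern was mainly neurological and neuropsychiatric.

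A worsened-from-baseline count also has a limit: it still includes patients who start normal and cross a threshold once among many repeated samples.

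**Conclusion.** The point holds as a presentation gap. As written, the any-grade laboratory tables can count unchanged entry abnormalities as toxicity, which raises both arms and weakens the ratio. At an assumed 10% v 20% of new abnormalities, a true ratio of 2.0 appears as 1.47 to 1.19 when 10 to 30% are abnormal at entry. The size rests on three assumptions: the entry-abnormal share, the new-abnormality rates, and grades that are not baseline-relative. Treating the hemoglobin and platelet floors as below normal is a further assumption, because site ranges are not given. SAP 12.2 plans no relative risk for laboratory data, so the effect is on how a reader compares the two percentages. No test, error rate, power or stopping decision depends on these tables. This is a cheap improvement, not a threat to the trial's conclusions.

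**What to change.** First adopt one laboratory baseline. Protocol 8.2.3.2 uses the last value up to first dose and averages same-date values. SAP 6.1 uses the last value up to randomization, with first dose as fallback. SAP 9 uses the latest value up to Day 1 and prefers retests.

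Then keep the worst-grade tables and add to SAP 12.2, for each graded parameter, by arm, in the safety population:

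1. a cross-tabulation of baseline grade by worst on-treatment grade, in the style of SAP 12.3 and 12.4;
2. the number and percentage of patients whose worst grade exceeds their baseline grade, placed beside the existing any-grade and Grade 3/4 counts.

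A footnote should say for which parameters, if any, the grade already allows for an abnormal baseline. The data are already collected, since baseline laboratory tests are required before randomization. The cost is some programming and slightly larger tables.

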### **8.2.6 Data recording and display**

Frequency tables will be tabulated (by treatment group or otherwise) for all categorical variables by the levels of the variables as they appear on the CRF (with %). Categories with a text field specification will be tabulated as categories and then supplemented by a listing with the following information for the patients fulfilling the condition for the specification (patient id, institution, treatment group, value of the item and text field contents).

Dates relating to events prior to entry will be presented as the delay in days (or weeks, months, or years) between the past event and the date of entry (date of randomization – date of past event + 1) and presented using the median and range as well as mean and standard deviation. For example, on the randomization checklist, the date of last administration of prior treatment (or the date of first diagnosis of the cancer) will be presented as the time elapsed (in days, weeks, months or years, as appropriate) since the day of the last administration and the date of entry on study (date of randomization – last administration/diagnosis +1).

Other delays (e.g. re-treatment delays) are presented as continuous variables using the median and range as well as mean and standard deviation.

Continuous variables for which a coding system exists (such as for laboratory data) will be recoded into categories (for adverse events, the grading scale specified in the protocol will be used). Whenever no specific scale exists, lab data will be categorized based on the normal range: for example, below the lower normal limit (when appropriate), within the normal range, above the upper normal limit (ULN) and the degree to which it is above the ULN (for example  $> 2.5 \times \text{ULN}$ ,  $> 5 \times \text{ULN}$ ,  $> 10 \times \text{ULN}$ ). For laboratory data, the nadir is generally displayed. The nadir in a given cycle is the lowest laboratory value in that cycle; the overall nadir for a patient is the lowest laboratory value among all cycles.

Other continuous variables (for example age, dose ...) are presented using the median range (minimum, maximum), mean and standard deviation.

If appropriate, continuous data may also be presented in categories (for example, age may also be grouped in decades).

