- Continuous variables for which a coding system exists (such as for laboratory data) will be recoded into categories (for adverse events, the grading scale specified in the protocol will be used). Whenever no specific scale exists, lab data will be categorized based on the normal range: for example, below the lower normal limit (when appropriate), within the normal range, above the upper limit of normal (ULN) and the degree to which it is above the ULN (for example > 2.5 x ULN, > 5 x ULN, > 10 x ULN). For laboratory data, the nadir is generally displayed. The nadir in a given cycle is the lowest laboratory value in that cycle; the overall nadir for a subject is the lowest laboratory value among all cycles;
- Other continuous variables (for example age, dose ...) are presented using the median range (minimum, maximum), IQR, mean and standard deviation;
- If appropriate, continuous data may also be presented in categories (for example, age may also be grouped in decades);

- P-values will be rounded to 3 decimal places. P-values that round to 0.000 will be presented as '<0.001' and p-values that round to 1.000 will be presented as '>0.999';
- Confidence intervals (CIs) will be presented as 2-sided 95% CIs unless specified differently in specific analysis;
- All mean and median values will be formatted to one more decimal place than the measured value. Standard deviation values will be formatted to two more decimal places than the measured value;
- All percentages will be rounded to whole numbers and one decimal. The number and percentage of responses will be presented in the form xx (xx.y%), where the percentage is in the parentheses;
- All listings will be sorted for presentation in order of treatment arm, subject, and date of procedure or event;
- All analysis and summary tables will have the analysis population sample size (ie, number of subjects);
- The day of the first dose of any study drug will be defined as Day 1.

Dealing with Multiple Values on the Same Day for Lab and Vital Signs Parameters

In cases where multiple values for the same variable are collected on the same visit (including baseline visit and post-baseline visits), the arithmetic average will be calculated and used as the value for that day for mean changes in laboratory and vital signs parameters.

Definition of Baseline Observation

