12.2.2. Biochemistry

Creatinine, creatinine clearance, protein, albumin, total bilirubin, alkaline phosphatase, alanine aminotransferase (SGPT), aspartate aminotransferase (SGOT), glucose, sodium, potassium, chloride, total calcium, calcium, ionized, total magnesium, magnesium, ionized will be

summarized by the worst grade in each treatment cycle and by the worst grade overall. The worst grade of each biochemistry parameter will be calculated for each subject. Frequencies and percentages of Grade 1, 2, 3, 4 in each category will be tabulated. A column with pooled Grade 3 or 4 frequencies and percentages will also be displayed. In a separate table, the frequencies and percentages of subjects with at least one Grade ≥ 1 or one Grade 3 or 4 hematological or biochemistry toxicity will be presented.

For urea, urea nitrogen, uric acid, bicarbonate normal ranges will be used to determine the categories of below and above normal ranges.

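### The only continuous laboratory summary listed in SAP 12.2 is the lowest value, which as an overall summary cannot show toxicity for tests where high values are harmful

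*SAP*

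**What the plan says.** - **SAP 12.2 (Clinical Laboratory Evaluations)**, the parent of 12.2.1 Hematology and 12.2.2 Biochemistry, specifies two by-patient summaries. One is by grade: "The worst grades during the treatment period will be summarized by treatment arm". The other is numeric: "The nadir and overall nadir will be presented with median, range (minimum, maximum), IQR, mean and standard deviation". No test is excepted from the second, and no peak value is listed. Listings with abnormal flags are added.
- **SAP 6.1 (Analysis Conventions)** defines the terms. The cycle nadir is the lowest value in the cycle, and "the overall nadir for a subject is the lowest laboratory value among all cycles". Tests without a grading scale are to be put in categories around the normal range, including how far they lie above the ULN.
- **Protocol 8.2.6** has the same convention: "For laboratory data, the nadir is generally displayed", and "the overall nadir for a patient is the lowest laboratory value among all cycles".
- **SAP 12.2.2** names the graded biochemistry tests, beginning "Creatinine, creatinine clearance, protein, albumin, total bilirubin, alkaline phosphatase, alanine aminotransferase (SGPT), aspartate aminotransferase (SGOT), glucose", to be "summarized by the worst grade in each treatment cycle and by the worst grade overall". Urea, urea nitrogen, uric acid and bicarbonate are instead classed as below or above the normal range.
- **SAP 12 (introduction)** says safety is reported for the whole study and by treatment period.

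**The concern.** A nadir is the right extreme for neutrophils, platelets or haemoglobin, where harm is a fall. Applied to a liver enzyme or to creatinine, the same rule picks the patient's most normal result. A hepatic or renal peak then has no effect on the overall numeric table, and a reader comparing arms there sees nothing of it.

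There is a second, smaller issue. The minimum of a series tends to fall as the series lengthens. Biochemistry is scheduled before every maintenance cycle (Protocol 6.2.2 and 6.2.3), and the planned number of cycles differs by arm. An overall nadir can therefore differ between arms because of the number of tests alone.

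At stake is the readability of the laboratory safety tables. No efficacy result depends on them.

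**Working it through.** The plan gives no figure to reproduce. The check has three parts.

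**1. Direction, test by test**

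| Tests | Harmful direction | What the overall nadir shows |
|---|---|---|
| ANC, WBC, platelets, haemoglobin, albumin, protein, creatinine clearance | low | the worst value: correct |
| Creatinine, bilirubin, ALP, ALT, AST, urea/BUN, uric acid | high | the most favourable value |
| Sodium, potassium and other electrolytes, calcium, magnesium, glucose | either | one of two harmful directions |

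SAP 12.3 explicitly plans observed values and change from baseline for vital signs. SAP 12.2 has no matching line for laboratory tests. SAP 6.1 mentions mean changes in laboratory parameters, but only when describing how to average multiple values.

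**2. Can the overall nadir register a peak?**

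By definition it cannot: a patient with one value at 10 x ULN and the rest normal has a normal overall nadir.

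A simulation shows the same at group level. All its inputs are assumptions, none from the documents: ALT = 0.6 x ULN x exp(b + e), with between-patient SD of b 0.35, within-patient SD of e 0.25, and 18 values per patient. In 20% of patients one value is multiplied by 8.

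| | No rise | 20% with one 8-fold rise |
|---|---|---|
| Median overall nadir (x ULN) | 0.38 | 0.38 |
| Share with maximum > 3 x ULN | 0.1% | 17% |

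**3. Dependence on the number of tests**

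For n independent standard normal values, E(min) = -n x integral of z phi(z) Phi(z)^(n-1) dz. This gives -1.27 (n=6), -1.42 (n=8), -1.49 (n=9), -1.70 (n=14) and -1.87 (n=20).

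Scheduled biochemistry after baseline is one draw at week 4, one per maintenance cycle and one at end of treatment (Protocol 6.2.1 to 6.3.1). The difference in E(min), marizomib minus control, with no drug effect is:

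| Scenario | Draws, control vs marizomib | Shift (SD) |
|---|---|---|
| Full course in both: 6 vs 18 cycles | 8 vs 20 | -0.44 |
| Control uses the tolerated 12 TMZ cycles | 14 vs 20 | -0.16 |
| Control completes 6 cycles; marizomib limited by the cut-off (below) | 8 vs 9 | -0.06 |
| Marizomib patient stops after 4 cycles | 8 vs 6 | +0.16 |

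The third row comes from the dates. The primary analysis uses the 28 APR 2020 cut-off, with 616 randomized (SAP 2). Protocol 1.1 reports 286 enrolled by 10 Jul 2019, read here as referring to this trial. That leaves 616 - 286 = 330 patients (330/616 = 54%) who entered within 293 days of the cut-off. After 6 weeks of radiotherapy and a 4-week break (70 days), (293 - 70)/28 = 7.96, so at most 8 maintenance cycles can have started. With the week 4 draw that is 9 values.

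The log-normal model, with within-patient SD 0.15 to 0.40, behaves the same way. The marizomib/control ratio of median overall nadir is 0.92 to 0.80 for 18 vs 6 values, about 1.00 for 6 vs 6, and 1.04 to 1.10 for 4 vs 6.

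**The case against.** The strongest reply is that high-side toxicity is already well covered. The worst-grade tables by arm name creatinine, bilirubin, ALP, ALT and AST, both per cycle and overall, with grade 3/4 pooled. SAP 6.1 provides above-ULN categories for tests without a scale, and abnormal values are flagged in listings. With one scheduled draw per cycle, the cycle nadir is usually that cycle's only value, so a peak would appear as the maximum of that cycle's range. The nadir is only said to be generally displayed, so other numeric tables are not ruled out. By-period reporting is already the stated rule. The adverse events of special interest are neurological, and none depends on these tables.

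All of this stands, and it limits the point. A reader might infer that the SAP summarises laboratory safety only by the lowest value and so hides liver or renal toxicity. The documents do not support that.

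What the reply leaves untouched is the overall nadir itself. It is a stated summary, applied to every test, and it carries no toxicity information where harm is high. Urea, urea nitrogen and uric acid have no worst-grade table, so they lean more on it. Where a cycle includes an unscheduled test on another day, the cycle nadir also keeps the lower value.

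**Conclusion.** The point holds as a minor to moderate reporting flaw in the safety tables. It is confined to the continuous overall summary: wrong direction for tests where high values are harmful, half the picture for two-sided tests, and correct for haematology, albumin, protein and creatinine clearance. It matters most for the ungraded tests. That the nadir is the only continuous summary rests on what SAP 12.2 lists.

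The overall nadir is also not comparable between arms when the number of tests differs. A reader might go further and infer that it makes the longer-treated marizomib arm look better, by about 0.44 SD. That figure needs completed courses of 18 and 6 cycles. The early cut-off, the tolerance of up to 12 TMZ cycles in control, and the SAP's own note in section 3 that marizomib exposure fell below plan all work against it, and the sign reverses if marizomib patients have fewer values. Actual test counts are not given, so the direction is unknown. The SD figures also assume independent values within a patient; correlation would shrink them relative to the total SD.

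**What to change.** In SAP 6.1 and 12.2, replace the general nadir rule with the extreme in the harmful direction:

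- **Minimum** for haematology, albumin, protein and creatinine clearance.
- **Maximum**, as a multiple of ULN where suitable, for creatinine, bilirubin, ALP, ALT, AST, urea/BUN and uric acid.
- **Both** for electrolytes, calcium, magnesium and glucose.

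State in 12.2 that these summaries follow the by-period reporting of SAP 12, so that the arms are compared over the concomitant and adjuvant TMZ periods they share. Show the number of values per patient alongside, because counts can still differ within a period.

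The cost is SAP wording and a change in the laboratory table programs. The long-term follow-up report repeats the whole of SAP 12, so the change would serve both reports.
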